1.3.1 Preclinical Testing for Axoguard® Nerve Cap

Comprehensive in vitro and in vivo biocompatibility evaluations provide support that Axoguard[®] Nerve Cap is safe for use in humans. Additionally, in vivo testing utilizing well established and validated animal models has demonstrated efficacy in its intended use to reconstruct and repair peripheral nerve

discontinuities; and support axonal regeneration of peripheral nerves following traumatic or oncologic nerve amputations.

Additionally, in vivo testing utilizing well established and validated animal models has demonstrated efficacy in reduced behavioral pain responses and increased optical density of the regenerating nerve stump resulting in the reduced likelihood of symptomatic neuroma formation and related pain following traumatic or oncologic nerve amputation. 22, 23

1.3.2 Manufacturing Controls

Axoguard® Nerve Cap is manufactured in accordance with current good manufacturing practices (cGMPs) for medical devices. The biomaterial undergoes a thorough disinfection, decellularization, and viral inactivation process. As a final step in the process, the biomaterial is sterilized via validated sterilization methods and then is vacuum pressed prior to packaging. To confirm biocompatibility, the material is tested by accredited, independent laboratories, using testing methods based on international standards and FDA guidance.

Axoguard® Nerve Cap has been sterilized using an established ethylene oxide (EO) cycle that has been validated to a sterility assurance level (SAL) of 10⁻⁶ in conformance with ISO standards.²⁴

1.3.3 Previous Clinical Experience General Use

To date, there has been no published clinical data collected for the use of Axoguard® Nerve Cap. This pilot study will serve to provide early feasibility data on patient reported outcomes for the treatment of symptomatic neuroma. The SIS material used in the design of the Axoguard® Nerve Cap is the same used in the design of the Axoguard® Nerve Protector and the Axoguard® Nerve Connector (K132660 and K162741 respectively), and are commercially available products for peripheral nerve repair.

1.3.4 Published Clinical Studies

As noted above, to date there has been no published clinical data collected for the use of Axoguard® Nerve Cap.

The use of SIS source material provides an environment for supporting natural tissue repair and without limiting vascularity throughout the implant.^{26, 27}.

Axoguard® Nerve Connector:

In previous clinic studies the Axoguard® Nerve Connector demonstrated promising benefits over direct repair in alleviating tension through the nerve's full range of motion and at the nerve site; while allowing vascular channels to remain open.²⁸

Axoguard® Nerve Protector:

In previous clinic studies the SIS material used in nerve repair with the Axoguard® Nerve Connector demonstrated promising benefits over repair with reconstituted collagen implant by preserving the extracellular matrix to support the natural healing process, retaining non-collagenous components that support host tissue response, and in providing an environment for natural tissue repair. ^{26,29,30,31,32}

2. STUDY OBJECTIVES

2.1 Primary Objective

The primary efficacy objective of the pilot phase of this study is to evaluate the difference in pain scores from baseline at 3 months for subjects receiving Axoguard® Nerve Cap; The primary efficacy objective of the comparative phase is the difference in pain assessments at 12 months between the two study groups (Axoguard® Nerve Cap vs standard neurectomy).

The aim is to see a reduction in pain caused by symptomatic neuroma, improved quality of life, reduction in the use of or strength of pain medication used to treat neuroma pain, and a reduction in recurrence of symptomatic neuroma within 3 months.

2.2 Secondary Objectives

[figure not shown]
The secondary objectives of this study are to compare degree of recovery over time (reduction in pain); quality of life data;

3. STUDY DESIGN

3.1 Description of Design

This is a multicenter, prospective, randomized, controlled, subject blinded comparative parallel group study in patients presenting with symptomatic neuroma (verified by diagnostic block or imaging (US or MRI confirmation) with a baseline pain level of \geq 65 mm on a 100 mm Visual Analog Scale (VAS) during screening. Fifteen (15) pilot subjects will receive the Axoguard® Nerve Cap in the pilot phase of the study. In the comparative phase of the study, approximately 86 adult subjects meeting inclusion/exclusion criteria will be centrally randomized in a 1:1 ratio to receive either Axoguard® Nerve Cap or neurectomy. This study design overview is found in Figure 3.1. This study is intended to collect post-operative data as well as physician experience surveys on the clinical use of Axoguard® Nerve Cap to evaluate its safety and performance as compared to subjects receiving neurectomy.

Figure 3.1. Study Design

This study will consist of a total of 8 visits

This study will be conducted in

accordance with the FDA regulations21 CFR Parts 50 and 56 and current cGCP requirements as described in the ISO 14155:2011 standards, applicable IRB regulations.

3.2 Study Treatment - Identification of Products

3.2.1 Study Product

Description: Axoguard® Nerve Cap is a surgical implant that is a tubular device with one open end, one sealed end (cap) and internal channels designed to provide protection for a peripheral nerve end or stump where repair is unattainable or not desired. The device isolates the nerve stump from the surrounding soft tissue bed by pulling the nerve into the tube and suturing the nerve within the cap. The end of cap has a suturable tab to allow the surgeon to suture the device to surrounding tissue.

Axoguard® Nerve Cap is provided sterile, for single use only, and offered in a variety of sizes to allow the surgeon to choose the appropriate size to address the injured tissue. Multiple patient labels with product code, lot number and expiration date are provided for subject records.

Federal (U.S.A.) law only allows Axoguard® Nerve Cap to only be sold under or by the order of a physician. This product is intended for use by trained medical professionals only.

3.2.2 Control

Description: Standard surgical treatment with neurectomy.

Neurectomy is a surgical treatment for symptomatic neuroma. It entails neuroma excision with high transection of the nerve. The goal is to relocate the nerve stump proximally into an area more protected by muscle and soft tissue, where it is less likely to become irritated and symptomatic.³³

3.3 Study Population

Adult male and female subjects (age \geq 18 years old) with symptomatic neuroma in the foot or ankle to at least one nerve where the nerve cannot be repaired to a distal nerve end.

3.4 Eligibility Criteria

3.4.1 Informed Consent

Authorized written informed consent (witnessed, where required by law or regulation) will be obtained from all subjects before any study related procedures are performed. Investigators may discuss the availability of the study and the possibility for entry with a potential subject prior to obtaining consent. However, informed consent must be obtained and documented on a written IRB approved consent form prior to initiation of any procedures that are performed solely for the purpose of determining eligibility for research. The site Investigator(s) has both ethical and legal responsibility to ensure that each subject under consideration for enrollment is given a full explanation of the study. This shall be documented on a written Informed Consent Form (ICF), which shall be approved by the same Institutional Review Board/Independent Ethics Committee (IRB/IEC) responsible for approval of this protocol. Each ICF shall include the elements required by Food and Drug Administration (FDA) regulations in 21 CFR Part 50, and current Good Clinical Practices (GCP) as described in the ISO 14155:2011 standard; and must adhere to the ethical principles that have their origin in the Declaration of Helsinki. The Investigator agrees to obtain approval from the Sponsor of any written ICF used in the study, prior to submission to the IRB/IEC.

Once the appropriate essential study information has been provided to the subject, fully explained by the Investigator (or qualified designee) and it is agreed that the subject understands all associated risks with participating on the study, the IRB/IEC –approved written informed consent form shall be signed and dated by all applicable parties in accordance to what is required by the IRB/IEC. The subject will be given a copy of the signed informed consent form and the original will be kept on file by the site Investigator. Explanation of study and the signing of the informed consent shall occur prior to the subject's participation in the trial.

3.4.2 Inclusion Criteria

To be considered for enrollment, subjects must meet the following inclusion criteria:

Table 3.4.2-1: Inclusion Criteria

Potential Subjects must:

- 1. Be able and willing to provide documented informed consent prior to the conduct of any study procedures;
- 2. Be an adult male or non-pregnant female \geq 18 years of age;
- 3. Report baseline pain scores of \geq 65mm on a 100mm Visual Analog Scale (VAS) at screening;
- 4. Have a documented diagnosis of symptomatic neuroma of at least one interdigital nerve in the foot which cannot be repaired to a distal nerve end;
- 5. Must have the following:
 - Pain with at least 3 of the following characteristics: burning, sharp, shooting, electric, parasthesias, numbness, cold intolerance;
 - Symptoms in a defined neural anatomic distribution
 - History of nerve injury or suspected nerve injury

Must have at least 1:

- Positive response to local anesthetic injection
- US or MRI confirmation of neuroma
- 6. Be candidates indicated for surgery to address a symptomatic neuroma;
- 7. Have sufficient healthy soft tissue available to adequately cover the Axoguard® Nerve Cap;
- 8. In the surgeon's opinion, be likely to achieve complete resection of the symptomatic neuroma and be able to undergo implantation with the Axoguard[®] Nerve Cap or complete the neurotomy procedure in the control group;
- 9. Be willing and able to comply with all aspects of the treatment and evaluation schedule over a 12-month duration.

3.4.3 Exclusion Criteria

To be included in the study, the following criteria must not occur:

Table 3.4.3-1 Exclusion Criteria

Potential subjects must not:

- 1. Have undergone surgical treatment of pain from symptomatic neuroma in the target nerve(s)on three or more occasions;
- 2. Have biomechanical pathology and associated pain (such as plantar fasciitis, bursitis, sesamoid bone pain, tendinitis, etc);
- 3. Have a life expectancy of less than 12 months;
- 4. Have a history of or planned radiotherapy in the area of the end-neuroma;
- 5. be contraindicated for soft tissue implants.; this includes but is not limited to any pathology that would limit the blood supply; compromise healing or indicate the presence of a local infection;
- 6. Have a history of chronic ischemic conditions of the extremity;
- 7. Have a diagnosis of type 1 Diabetes Mellitus; or uncontrolled Type 2 Diabetes Mellitus (at the discretion of the investigator);
- 8. Have a history of diabetic neuropathy;
- 9. Be undergoing or expected to undergo treatment with chemotherapy, radiation therapy, or other known treatment which affects the growth of neural and/or vascular system;
- 10. Be immunosuppressed, immunocompromised or have planned immunosuppressive therapy within 12 months following the study procedure;
- 11. Have a History of congenital neuropathy or compressive neuropathy affecting the target limb;
- 12. Have a history of prior surgical management of more proximal compressive neuropathies or spinal conditions (e.g. spinal stenosis) not related to the symptomatic neuroma that affect the target limb;
- 13. Currently use or likely need to use medication during the study known to impact nerve regeneration or to cause peripheral neuropathy;
- 14. be pregnant or plan to become pregnant during the duration of the study;
- 15. Be or have been enrolled in another interventional study within 30 days prior to consenting;
- 16. Have a known allergy to anesthetic agents;
- 17. Have a known sensitivity to porcine derived materials; or
- 18. Be, in the opinion of the Investigator, unsuitable for inclusion in the study.

3.4.4 Enrollment in Study

3.4.4.1 Treatment of Multiple Neuromas

In instances where subjects have multiple neuromas in the foot/ankle, the surgeon must identify the target nerve for inclusion in this study, and agree to treat all additional neuromas as per the randomization assignment. Additionally, if subjects are diagnosed with bilateral neuromas (whether interdigital or elsewhere in the foot/ankle) each limb and all affected nerves must follow the same randomization assignment. Please note, for instances of bilateral neuromas, surgical treatment for each foot may be completed at the same time, but no later than 270 days after subject randomization.

For instances when surgical intervention cannot be completed for the contralateral foot by day 270, further surgical intervention is to occur after the subject has completed the study, or study participation must discontinue.

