3.4.4.2 Subject Screening and Numbering

After the subject has signed an IRB-approved informed consent form, he/she will be assigned a unique screening number. At each site, the screening numbers will start with S001. Subjects who meet the inclusion and exclusion criteria will be eligible for the study. In the comparative phase, randomization will occur intra-operatively, and a randomization number will be assigned to identify the enrolled subject.

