 $X_{optimal}$ = Score of the optimal foot health

 $S_{optimal}$ = Highest score of the new scale

Foot Function:

 $X_{worst} = 20$

 $X_{optimal} = 4$

 $S_{optimal} = 100$

Foot Health:

 $X_{\text{worst}} = 10$

 $X_{\text{optimal}} = 2$

 $S_{\text{optimal}} = 100$

Footwear:

 $X_{\text{worst}} = 3$

 $X_{\text{optimal}} = 15$

[figure not shown]
 $S_{\text{optimal}} = 100$

Foot Pain:

 $X_{\text{worst}} = 20$

 $X_{\text{optimal}} = 4$

 $S_{\text{optimal}} = 100$

Daily Pain Diary

A daily pain diary will be provided to each subject at the Screening visit (V1) and a new diary will be dispensed to the subject at Visits 2 through 7 to track incidence, frequency, and severity of pain (using a 10-point scale) daily. The diary will be reviewed and collected at each study visit (by the site team with the subject) prior to completing the scheduled pain assessments (VAS/PROMIS). The diary will also help track the use of subject pain medicine administration by reminding the subject to complete the Daily Pain Medication Diary for any pain medication/treatment taken by the subject at the time of the foot pain.

Daily Pain Medication Diary

A Daily Pain Medication Diary will be provided to each subject to take home and complete each day and will be reviewed at all visits. The subject will present the medication diary at each study visit for review by the site team and a new diary will be dispensed to the subject at each visit. The diary will be used to summarize pain medications by any use.

Opioid pain medications taken will be converted to morphine milligram equivalent (MME) where such conversions are available to summarize pain medications by quantity of use. For opioid and non-opioid pain medications, the Medication Quantification Scale⁴ (MQS) conversion will be used to convert medications to a comparable score. The MQS is a broader approach to quantifying medication consumption that captures non-opioid classes of medications without an equivalency to morphine. Unlike MME, two factors (detriment weight and dosage level) multiplied together scale the medication to a single score. Additionally, drugs will be categorized according to type of medication and the quantity taken will be summarized.

Recurrence of Symptomatic Neuroma

Subjects will be assessed for recurrence of symptomatic neuroma at the 3, 6, 9, and, 12 Month visits. The assessment intervals for each visit are as follows:

- Month 3 Visit: 6 Weeks after Operative Day 0 until Month 3 Visit

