- Month 6 Visit: Month 3 Visit until Month 6 Visit
- Month 9 Visit: Month 6 Visit until Month 9 Visit
- Month 12 Visit: Month 9 Visit until Month 12 Visit

A subject is considered to have had a recurrence of symptomatic neuroma if all of the following conditions are met:

 Subject experiences a pain level greater than 1 on the 10-point scale of the daily pain diary at least one time during the assessment interval

- The average daily dose of morphine (mg/day) calculated using morphine equivalent dosing during the assessment interval is higher than the average daily dose during the baseline interval (between Screening visit and Operative Day 0)
- VAS pain score is higher at assessment visit than at baseline visit

Adverse Event

An AE is defined as any untoward event (including abnormal lab findings) experienced by a subject (whether or not considered product-related by the site Investigator or Sponsor) after the patient consents to participate in the trial. All AEs that occur during or after study product implantation/device insertion must be recorded in the subject's medical record and reported on the adverse event CRF.

Serious Adverse Events

A serious adverse event (SAE) is any untoward medical occurrence that occurs per the following definition.

- Results in death:
- Is immediately life threatening in the opinion of the site Investigator, the participant was at substantial risk of dying at the time of the event, or use or continued use of the device might have resulted in the death of the subject;
- Requires in-patient hospitalization or prolongation of existing hospitalization.
 Complications that occur during hospitalization are adverse events, and if a complication
 prolongs hospitalization, the event is considered serious. Emergency room visits that do
 not result in overnight hospital admissions should be evaluated for one of the other
 serious outcomes (e.g., life-threatening; required intervention to prevent permanent
 impairment or damage);
- Results in a Congenital Anomaly / Birth Defect suspect that exposure to the device prior to conception or during pregnancy may have resulted in an adverse outcome in the child; or
- Requires Intervention to Prevent Permanent Impairment or Damage medical or surgical
 intervention was necessary to preclude permanent impairment of a body function, or
 prevent permanent damage to a body structure, either situation suspected to be due to the
 use of the device.

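### Staged surgery on the other foot is allowed to Day 270, but the recurrence rule sets aside six post-operative weeks only after the index operation

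*Protocol*

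**What the plan says.** Protocol 3.4.4.1 requires both feet to follow the same assignment and states that "surgical treatment for each foot may be completed at the same time, but no later than 270 days after subject randomization". In the comparative phase "randomization will occur intra-operatively" (Protocol 3.4.4.2), so the limit is Day 270 after the index operation.

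SAP section 6, under Recurrence of Symptomatic Neuroma, sets four assessment intervals. Only the first has a delayed start: "Month 3 Visit: 6 Weeks after Operative Day 0 until Month 3 Visit". The other three simply join successive visits and leave nothing out; the last of them, which serves the tested endpoint, reads "Month 12 Visit: Month 9 Visit until Month 12 Visit".

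Recurrence requires all three of the following:

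1. "Subject experiences a pain level greater than 1 on the 10-point scale of the daily pain diary" (a single occurrence in the interval is enough).
2. Mean daily morphine-equivalent dose "during the assessment interval is higher than the average daily dose during the baseline interval".
3. VAS at the visit above VAS at baseline.

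SAP 9.2.1 tests recurrence at Month 12 and judges each visit independently. SAP 7.2 bases all analyses on the primary neuroma. The VAS asks for current pain (Protocol 3.6.1), and neither diary is limited to the target foot. The legible text has no rule for data that follow a later operation on the other foot.

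**The concern.** The six-week start keeps the immediate recovery from the index operation out of the recurrence assessment. The SAP gives no reason for it, but surgical pain and opioid use are the natural one. A second operation brings the same kind of pain and opioid use. It may fall in any interval, and nothing is set aside for it.

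The analysis is meant to describe the primary neuroma, while two of the three recurrence conditions use measures that cannot tell one foot from the other. In a staged case those two conditions may reflect recovery from a different operation. The opioid endpoints and the diary AUC take in the same episode. At stake are the clarity of the recurrence result and some loss of sensitivity in these secondary endpoints.

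**Working it through.** The plan gives no figure on this point to reproduce. The check is day arithmetic.

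**Inputs from the documents.** Nominal visit days are 90, 180, 270 and 360 (Protocol Appendix B). The exclusion is 6 weeks = 42 days (SAP section 6). The latest contralateral surgery is Day 270 (Protocol 3.4.4.1). Windows for Months 3 to 12 are ±14 days (Protocol contents list). There are 86 / 2 = 43 subjects per arm.

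**Step 1. Reach of the six weeks after surgery on day s.** Overlap = min(interval end, s + 42) − max(interval start, s), or zero if negative.

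| Surgery day | Six weeks end | Overlap with recurrence intervals |
|---|---|---|
| 0 | 42 | none |
| 42 | 84 | Month 3: 42 of 48 days (88%) |
| 90 | 132 | Month 6: 42 of 90 (47%) |
| 150 | 192 | Month 6: 30 of 90 (33%); Month 9: 12 of 90 (13%) |
| 180 | 222 | Month 9: 42 of 90 (47%) |
| 228 | 270 | Month 9: 42 of 90 (47%); Month 12: none |
| 256 | 298 | Month 9: 14 of 90 (16%); Month 12: 28 of 90 (31%) |
| 270 | 312 | Month 12: 42 of 90 (47%) |

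Only surgery on the same day as the index operation is fully covered by the present rule. The Month 12 interval is reached when s + 42 exceeds the day of the Month 9 visit, so after Day 270 − 42 = 228 nominally, or after Day 214 to 242 across a visit on Day 256 to 284.

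For Day 270 surgery, visit windows move the Month 12 share as follows. The highest is 42 / (346 − 270) = 42/76 = 55% (Month 9 visit on Day 270, Month 12 visit on Day 346). The lowest is (312 − 284) / (374 − 284) = 28/90 = 31%.

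**Step 2. Opioid condition.** Added mean = days × dose / interval length. The courses are assumptions: 3 days at 30 mg/day gives 3 × 30 / 90 = 1.0 mg/day, and 14 days at 40 mg/day gives 14 × 40 / 90 = 6.2 mg/day. With zero baseline use, any dose meets the condition. With no other opioid use in the interval, a baseline mean of 6.2 mg/day or more would not be exceeded by these courses.

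**Step 3. Diary condition.** One score above 1 is enough.

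**Step 4. VAS.** From Day 270 surgery to the Month 12 visit: 346 − 270 = 76 to 374 − 270 = 104 days, both beyond 42. Earlier visits can fall inside the six weeks: surgery on Day 150 is 30 days before a Day 180 visit.

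**Step 5. Diary AUC.** Assume 2 to 5 extra points for 14 to 42 days. The addition is 2 × 14 = 28 to 5 × 42 = 210 point-days, or 28/360 = 0.08 to 210/360 = 0.58 points on an affected subject's 12-month mean.

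**Step 6. Chance imbalance.** The share of staged cases is not given. For an assumed share p, the 95% range of the between-arm difference is ±1.96 × √(2p(1 − p)/43): ±9 percentage points at p = 5%, ±17 at p = 20%.

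**The case against.** Much of the case on the other side stands.

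- **All three recurrence conditions are required.** Protocol 3.4.2 sets entry VAS at 65 mm or more, so the third condition asks for pain above an already high baseline. At Month 12 it is measured at least 76 days after the latest permitted surgery. A reader might infer that the second operation by itself produces recurrences; the definition does not support that. The diary condition is also so easily met that a second operation may often change nothing there.
- **The six-week start applies to one interval of one endpoint.** A reader might infer a general post-operative exclusion that the SAP forgot to repeat. There is none: the AUC runs over the full 12 months and keeps the index recovery, and the Month 12 MME and MQS endpoints have no stated averaging interval. Dropping only the second recovery from the main AUC would create a new inconsistency.
- **The primary endpoint is little exposed.** A reader might infer a biased primary result. A similar shift in both arms cancels in the difference, and its sign is uncertain, because treating the other foot may lower a VAS that is not foot-specific. Contralateral surgery follows the randomized assignment, so it is arguably part of the assigned strategy. Setting later VAS values to missing would not help: SAP 7.3 imputes missing primary values and the legible SAP names no mixed model, which appears only in Protocol 5.7.4.
- **There is a partial safeguard.** The per-protocol population in SAP 7.4.3 removes subjects with confounding conditions, and its wording is open-ended. It does not name contralateral surgery, drops whole subjects, and serves sensitivity analyses only.

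What remains is that the recurrence rule, as written, counts surgical pain and opioid use from the other foot in two of its three conditions.

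**Conclusion.** The point holds for the diary and opioid conditions of the recurrence endpoint. It also applies, as added noise, to the opioid and diary-AUC comparisons. For the tested Month 12 recurrence it concerns surgery after about Day 228 and touches at most 42 of 90 nominal days. The opioid condition is at risk mainly in subjects with little or no baseline opioid use.

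Both feet share one assignment, so the expected effect is dilution. Bias would need an imbalance between arms in staged cases; chance could produce one at this sample size, but the documents give no share from which to size it. The opioid courses, diary increments and shares above are assumptions. The conclusion rests on the legible SAP text, in which the recurrence definition and its intervals can be read in full. It is worth correcting before unblinding, so that affected subjects are not handled case by case, but it does not call the primary analysis into question.

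**What to change.** Leave the surgical schedule unchanged.

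1. Capture the date of any later neuroma surgery. Appendix B schedules Operative Information only at Visit 2, so it should not be assumed that this date is already collected; a field may be needed.
2. In SAP section 6, apply the same six-week exclusion after that date to the diary and opioid conditions of every recurrence interval, with the mean dose taken over the remaining days. Leave the VAS condition as it is.
3. As sensitivity analyses only: (a) repeat the MME, MQS and diary/VAS AUC comparisons without the six weeks after a staged contralateral operation, with AUC expressed per day observed; (b) name staged contralateral surgery as a confounding condition in the per-protocol sensitivity analysis. The primary VAS analysis stays unchanged.

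The cost is one date field, some SAP wording and programming, and a real loss of interval in affected subjects: up to 42 of about 90 days (47%), and for Day 42 surgery 42 of the 48 days in the Month 3 interval, which leaves 6. The SAP should say that recurrence is not evaluable when no diary days remain. The visit VAS at Months 6 and 9 stays exposed, which affects description only, since the recurrence test is at Month 12.
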